#### **Research Design and Methodology**

The overall goal of this study is to use findings from Phase 1 (See protocol number 2020-0017) to deliver and refine a tailored ESD violence prevention training for diverse trans women. Participants for Phase 2 (n = 48) will be recruited from online forums including social media sites (e.g., Facebook, Twitter), banner ads on social networking/dating sites (e.g., Scruff, BGC Live, OK Cupid, Lex) that are trans-inclusive and through dissemination of paper and/or electronic recruitment flyers with leaders of community organizations that connect transgender individuals (e.g., AVP; Callen Lorde, Trans-lantinx network). Participants from prior studies who consented to future contact will be sent the study flyer by email. The proposed curriculum will be systematically refined based on delivery of the intervention to 3 groups of 16 TW each in a 20-hour training program, in 5 4-hour sessions. We have contracted with Prepare, Inc., the New York City chapter of IMPACT International to deliver the tailored ESD violence prevention intervention. IMPACT is an international ESD violence prevention organization with chapters across the United States. Prepare, Inc. will provide facilitators who have completed IMPACT's nationally standardized ESD violence prevention program requirements that include receipt of over 100 hours of training. IMPACT training is open to trans and cisgender women. The extensive training of IMPACT facilitators promotes intervention efficacy, while the risk of potential bias conferred by their experience with a pre-existing curriculum is mitigated by our community-engaged approach (i.e., TW community members, service providers, and scientists [PI and Co-I] collectively shape the content of the final tailored ESD intervention, and TW co-facilitators will be present in every training session). Prior to the start of group, facilitators will review the tailored curriculum in detail and attend 2-3 supervision/training meetings with the PI. These meetings will consist of reviewing the curriculum, role-plays of critical intervention components, and discussion of questions or concerns. The primary outcome of Aim 2 is to evaluate our ability to recruit our target (n = 48) and retain >75% over the course of the intervention. Successful completion of the pilot trial, including meeting or exceeding these benchmarks for success, will determine the feasibility and acceptability of recruiting participants into a future RCT. Preliminary efficacy of the tailored ESD violence prevention intervention will be evaluated as an exploratory aim. Participants enrolled in the pilot trial will be administered a battery of validated baseline questionnaires at baseline, immediately following the course, and 6 months after course completion (see Assessment Packet in attached below) including: - Demographics - Social Class Ladder- Community Ladder- Service Utilization Form - Sexual experiences Survey - Everyday Discrimination

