
Scale- Conflict Tactics Scale - Gender Minority Stress Risk and Resilience Scale - Post Traumatic Stress Disorder Symptom Checklist for DSM-5 (PCL-5)- Sexual Assertiveness Questionnaire- Resistance Tactics Survey- Dating Self-Protection - Illinois Rape Myth Acceptance - Resistance Self-Efficacy - Personal Progress- Transgender Congruence Scale - Depression Anxiety and Stress Scale - Quick Drinking Screen - DAST-10Brief acceptability checklists will be administered after each course session, which will contain a brief list of topics covered during that training session and participants will indicate which of the topics they felt were adequately covered (See page 38 of Assessment Packet, "Satisfaction and Fidelity Forms" for example items and formatting of this checklist). Lastly, an exit interview will be scheduled on the final day of the course, and will take place over the weeks immediately following the completion of the course. Interviews will be video recorded using the Zoom videoconferencing platform. The video-recorded qualitative interviews will be recorded and transcribed verbatim using the Zoom transcription function (omitting identifying information) and verified for accuracy. We will use three strategies to improve retention, based on an intensive evidence-based follow-up protocol with which the PI has considerable experience. First, participants will be compensated for completion of the assessment appointments at increasing increments over time (i.e., \$40 for baseline, \$30 for follow-up immediately after the course and \$30 for the exit interview after the course, \$80 for 6-month follow-up). Second, at baseline, participants will be asked to provide extensive locating information and to provide names of two local persons to be contacted in the event that the participant cannot be reached. This information will be updated at the time of follow-up survey administration. Third, participants will receive \$10 cash for each of the five session acceptability checklists they complete (one per session attended- up to \$50 total) which will be distributed at session 3/5 (up to \$30) and 5/5 (up to \$20). Analyses will be of two primary types: (a) examinations of whether feasibility targets were met across a variety of measures; and (b) examinations of the efficacy of the tailored ESD violence prevention intervention. We will use repeated measures one-way ANOVA to test if the tailored ESD curriculum has statistically significant effect on measures of behavioral and psychological/attitudinal change. If a significant effect is detected, we will use Tukey's pairwise-comparison procedure to compare all treatment means, with a 95% family confidence coefficient. To assess changes in exposure to victimization, we will collapse into three levels: (a) no history of victimization; (b) moderate victimization; (c) severe victimization. For this categorical data, a chi-square test of independence will be performed to compare posttreatment vs. pre-treatment, and 6-month FU vs. pre-treatment respectively to assess the preliminary efficacy of the program, with a family-wise type I error controlled at 0.05 using Bonferroni procedure. Our efficacy outcomes are exploratory and powered to detect large effect sizes. In the largest scale RCT of an ESD violence prevention program to date, rates of completed assault among women receiving resistance training were reduced by half at 1-year follow-up. However, as there are no existing studies that report on ESD efficacy among TW, we will use results of our exploratory efficacy analysis to shape power analyses for a subsequent, fully powered, RCT

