List all research related procedures/data collection methods involving interaction or intervention with participants; use the Add New Procedure and Risk button to add each method. or intervention with

participants; use the Add New Procedure and Risk button to add each method.	
Procedure	Tailored IMPACT Basics Intervention
Where it will take place?	IMPACT Basics Course will take place at a well ventilated space centrally located and furnished by God's Love We Deliver ([name]).
When it will take place?	There will be three pilot series that will take place as part of this study. Series 1: 7/11/21, 7/18/21, 7/25/21, 8/1/21, 8/8/21Series 2: 9/19/21, 9/26/21, 10/3/21, 10/10/21, 10/17/21Series 3: 11/14/21, 11/21/21, 12/4/21, 12/11/21, 12/19/21As participants are recruited, they will be assigned to one of the three series based on their availability.
Frequency	As this study involves iterative tailoring of the intervention curriculum, the pilot intervention will be rolled out in 3 groups. Each pilot intervention will be followed by tailoring before rolling out the intervention to the following group. Thus, ESD violence prevention programming will take place 3 times, but each participant will only participate in one of the series.
Is procedure optional for participants?	Yes
Associated risk or discomfort	It is possible that participants may experience some discomfort while participating in the ESD violence prevention program.Due to the COVID-19 pandemic, in-person participation poses additional risk to participants.
Anticipated severity of risk or discomfort	No more than minimal risk
Expected frequency of risk or discomfort	The schedule for each of the 3 ESD series is outlined above. Participants will be assigned to one of the three series based on best availability match, so frequency of risk or discomfort is five times for five course sessions.

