Risk reduction or mitigation method	By contracting with Prepare, Inc., an organization with over 30-years of experience providing ESD training to diverse clientele, we are ensuring that every possible step is taken to manage the natural discomfort that may arise when learning new verbal and physical skills in a personal safety program. During all group sessions the lead instructor will stand near the participant providing ongoing support, encouragement, and verbal prompting to participants, as needed, during role-play scenarios. The behavior of all instructors in conducting and coaching participants through role plays will be carefully thought out and implemented. At no time will participants role-play with one another. Consent documentation will make it clear that participants may refuse to continue with the study at any time, without penalty. In addition, we will remind participants during the course of the group that they do not have to participate in any exercise or role-play that they do not wish to and may discontinue participation at any time. Participants who report or demonstrate any distress during class will be referred to counseling services at local agency with whom the PI has established linkages (The Center). Additional assistance in grounding and following a role-play scenario. All counseling resources are available to participants regardless of ability to pay.Regarding the risk of COVID-19 transmission during participants and research staff present during the ESD program sessions. Personal protective equipment will be made available for all attendees including hand sanitizer, gloves, face shields, and N95 respirator masks. All program sessions will take place in a well-ventilated area furnished by God's Love We Deliver (outside). Participants will remain 6 feet apart during sessions, with the exception of time limited physical defense drills.

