## DSMB?s prospectively identified criteria for discontinuing the study

Adverse Event (AE): Defined as any untoward medical occurrence in a patient or research subject administered a pharmaceutical product or other research intervention and that does not necessarily have a causal relationship with this treatment. An AE can therefore be any unfavorable and unintended sign (including an abnormal laboratory finding), symptom, or disease temporally associated with the use of a medicinal (investigational) product or research procedure, whether or not related to the medicinal (investigational) product or procedure. Negative events that occur during study involvement do not constitute adverse events unless they lead to physical harm (in which case the injury is the AE) or deterioration of mental health functioning (in which case the symptoms are the AE). Negative events that may potentially affect response to the intervention or study involvement should be reported as AEs. See IRB Reporting Requirements below for instructions on how to report these events. Examples might include legal problems or traumatic events. The program facilitator should query about adverse events (AEs) at every session by asking about any notable events since the last visit. These should be reviewed in a timely manner with the supervisor. Serious Adverse Event (SAE): An AE occurring in a patient or subject enrolled in a research study is serious if it results in any of the following outcomes: death, a life-threatening adverse drug experience, inpatient hospitalization or prolongation of existing hospitalization, a persistent or significant disability/incapacity, or is a congenital anomaly/birth defect.Unanticipated Problems Involving Risk (UPR): Defined as being (1) unexpected given the research procedures and characteristics of the population, (2) related (or possibly related) to participation in the research and (3) indicative that the research may place the subject or others at a greater risk of harm than was previously known. Examples of possible UPRs for psychotherapeutic interventions: 1. Psychosis or mania2. New onset or clinically significant exacerbation of a psychiatric disorder3. Suicide and suicide attemptsAn incident, experience, or outcome that meets UPR criteria generally will warrant consideration of substantive changes in the research protocol or informed consent process/document or other corrective actions in order to protect the safety, welfare, or rights of subjects or others. Examples of corrective actions or substantive changes that might need to be considered in response to an unanticipated problem include: modification of inclusion or exclusion criteria to mitigate the newly identified risks; implementation of additional procedures for monitoring subjects; suspension of enrollment of new subjects;suspension of research procedures in currently enrolled subjects;modification of informed consent documents to include a description of newly recognized risks; and provision of additional information about newly recognized risks to previously enrolled subjects. Reporting Requirement: All UPRs/AEs/SAEs, regardless of relatedness to the intervention, are to be reported to the local IRB as soon as possible, no later than 10 business days from the date the investigator or research staff becomes aware of the event/problem. Fill out an AE form, SAE form, and/or UPR form, obtain the study PI's signature, and submit to the Hunter IRB. Then forward each AE/SAE/ UPR form to Data Safety Monitoring Board as soon as possible. The study PI will maintain a record of all AEs/SAEs/ UPRs to report to the Hunter IRB in summary or table form at the end of the study. The PI will notify NIMHD of any UPR, AE, or SAE promptly via email. Protocol Deviation/ViolationA protocol deviation or violation is any change, divergence, or departure from the study design or procedures of a research protocol. Investigators are required to conduct their research according to the plans reviewed and approved by the IRB. Instances where this does not occur, either inadvertently due to circumstances beyond the investigator's control, or due to errors of omission or commission by research project staff, must be reported. Reporting Requirement: Fill out a Protocol Deviation/ Violation form, and submit to local IRB within 3 days of the occurrence (one day if there was harm to the participant). Also email the form (with encryption) to the PI and Study Coordinator, who will maintain a record of all Protocol Deviations/Violations to report to the Hunter IRB.

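### The only adverse-event question described asks about notable events; no described procedure asks directly about training injury, and symptom scores are not linked to AE recording

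*Protocol*

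**What the plan says.** **AE query.** The AE text appears six times in Protocol section 7 (Research Design - Risks and Benefits, under the stopping-rule and discontinuation headings) and once in section 16 (Privacy and Confidentiality). Each copy gives the same instruction: "The program facilitator should query about adverse events (AEs) at every session by asking about any notable events since the last visit".

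**AE definition.** The same paragraph defines an AE broadly, as any unfavorable sign, symptom or disease associated in time with a research procedure. It then says that negative events during the study are not AEs "unless they lead to physical harm (in which case the injury is the AE) or deterioration of mental health functioning"; in the second case the symptoms are the AE. The next sentence widens this: "Negative events that may potentially affect response to the intervention or study involvement should be reported as AEs". Its examples are legal problems and traumatic events.

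**Exposure.** Section 5 describes a "20-hour training program, in 5 4-hour sessions". Section 6 keeps participants 6 feet apart "with the exception of time limited physical defense drills". The course risks named there are COVID-19 and discomfort ("It is possible that participants may experience some discomfort while participating in the ESD violence prevention program"). Physical injury is not named.

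**Other data.** The questionnaire battery in section 5 includes the PCL-5 and the Depression Anxiety and Stress Scale. Section 6 schedules it at baseline, straight after the course and at 6 months. The form after each session is described as an acceptability checklist of topics covered. Distress reported or shown in class leads to a counseling referral.

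**The concern.** The instruction to the facilitator states a method, which is to ask about notable events. Much of what the protocol defines as an AE is a bodily injury or a change in symptoms. A participant asked whether anything notable has happened is likely to think of an assault, an arrest or a crisis. She may not mention a sore shoulder from a drill, or worse sleep and intrusive memories.

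The curriculum is revised after each of the three series, so harm missed in series 1 cannot inform series 2 or 3. Section 16 asks the DSMB to monitor non-serious AEs and to review the completeness and validity of the safety data, and both tasks depend on how AEs are elicited. The study has one arm and is meant to prepare an RCT. No control group would reveal under-recording, and a reader could take a nearly empty AE table as evidence that the course is safe.

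**Working it through.** The plan gives no figure on this point, so the check is a comparison of passages, followed by an illustration on assumed rates.

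**1. Which described procedure would pick up which kind of AE?**

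| Kind of AE under the protocol's text | Asked directly? | Other described route |
|---|---|---|
| Injury from a drill | No | Staff may see it; she may volunteer it |
| New or worse symptoms between sessions | No | Staff may see distress in class, but the stated action is referral, not AE recording |
| Symptom change from baseline to post-course or 6 months | Yes, by PCL-5 and Depression Anxiety and Stress Scale | No score change is defined as an AE; no route from scores to an AE form or the DSMB is stated |
| Legal problem or traumatic event that may affect response or involvement | Yes, by the notable-events question | None needed |

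The question fits the last row well. It reaches the first two only if the woman treats an injury or a symptom as a notable event.

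**2. How often is each asked?** The AE question is asked at 5 sessions per woman, and at 3 x 5 = 15 sessions in all. Symptoms are measured at 3 time points, 2 of them after training. Described direct questions on training injury: 0. The time of asking within a session is not stated. If it is at the start, training in session 5 (4 of 20 hours) falls after the last query.

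**3. What could under-recording do?** The documents give neither an AE rate nor a recording rate, so both are assumptions. Let p be the true proportion of the 48 women with a course-related injury or symptom worsening, and s the proportion of these who reach the AE record.

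- Expected number recorded = 48 x p x s
- Chance that none is recorded = (1 - p x s)^48

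| p | True cases (48p) | s = 0.3: recorded; chance of none | s = 0.6: recorded; chance of none | s = 0.9: recorded; chance of none |
|---|---|---|---|---|
| 0.05 | 2.4 | 0.7; 48% | 1.4; 23% | 2.2; 11% |
| 0.10 | 4.8 | 1.4; 23% | 2.9; 5% | 4.3; 1% |
| 0.20 | 9.6 | 2.9; 5% | 5.8; 0.2% | 8.6; below 0.1% |

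For example, with p = 0.10 and s = 0.3, (1 - 0.03)^48 = 0.232. The formula takes women as independent and all 48 as asked. Injuries seen by staff raise s, so the left-hand column is too pessimistic if most harm is visible in class.

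**The case against.** The strongest reply is that the question is not the only way an AE can come to light. The 10-business-day reporting clock starts when the investigator or staff become aware of an event, however they learn of it. The lead instructor stands near each participant in role-plays and could see an injury happen. The instruction is also not a verbatim script: it tells the facilitator to query about AEs, and being hurt in a drill is notable in ordinary speech. All of this stands. It limits the likely loss to harm that staff do not see and the woman does not volunteer. It does not supply a direct question.

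Two stronger readings are tempting, and the documents do not support them:

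- **A reader might infer that worsening mental health is never asked about.** It is asked about, by two symptom scales before and after training. The gap is that the scores are not linked to AE recording and say nothing about the weeks between sessions.
- **A reader might infer that a negative event is never itself an AE, so that the question misses everything the plan defines.** The sentence quoted above on events that may affect response or involvement says otherwise. An events question does elicit that class of AE. What remains is a tension between two adjacent sentences on when a negative event counts.

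It is also fair to say that the primary targets are recruitment and dropout, that no safety endpoint is stated, and that the session forms, interview guide and AE forms were not available to check. An injury item may exist in one of them.

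**Conclusion.** The point holds in a limited form. The one AE query described is an open question about notable events. No described procedure asks directly about injury from the physical drills. Symptom scores are collected at three time points without a stated link to AE recording. Under-recording is therefore possible, mainly for injuries unseen by staff and for symptoms that worsen between sessions.

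Its size is unknown. The percentages in the table show only that, at true rates of 5-10% with recording of 30-60%, an empty AE table would be weak evidence of safety. They are not estimates, and a reader should not infer that the counts will be biased by that amount. The conclusion also assumes that the Assessment Packet and AE forms, which are not in the documents, contain no direct injury item. This is a cheap improvement to safety data, not a flaw in the feasibility aims.

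**What to change.** In every copy of the AE text, keep the notable-events question and add two fixed yes/no items at each session:

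- (a) any injury, pain or physical problem during or since the last session;
- (b) any new or worse emotional symptoms since the last session.

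Record the no answers as well, and report each item over the number of women asked.

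Keep asking separate from classifying. Judge each yes against the protocol's own AE definition and do not count it automatically. Every AE, whatever its cause, goes to the IRB, the DSMB and the funder, so automatic counting would send ordinary soreness to all three. Do not remove notable events from AE status either. The sponsor must first reconcile the two adjacent sentences on when a negative event is an AE.

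The cost is a wording change and a short form at 15 sessions, at most 48 x 5 = 240 individual records, with more minor reports to review.

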# How frequently will the DSMB Quarterly meet?

Provide description of stopping rules and justification for the stopping rules

Adverse Event (AE): Defined as any untoward medical occurrence in a patient or research subject administered a pharmaceutical product or other research intervention and that does not necessarily have a causal relationship with this treatment. An AE can therefore be any unfavorable and unintended sign (including an abnormal laboratory finding), symptom, or disease temporally associated with the use of a medicinal (investigational) product or research procedure, whether or not related to the medicinal (investigational) product or procedure.Negative events that occur during study involvement do not constitute adverse events unless they lead to physical harm (in which case the injury is the AE) or deterioration of mental health functioning (in which case the symptoms are the AE). Negative events that may potentially affect response to the intervention or study involvement should be reported as AEs. See IRB Reporting Requirements below for instructions on how to report these events. Examples might include legal problems or traumatic events. The program facilitator should query about adverse events (AEs) at every session by asking about any notable events since the last visit. These should be reviewed in a timely manner with the supervisor. Serious Adverse Event (SAE): An AE occurring in a patient or subject enrolled in a research study is serious if it results in any of the following outcomes: death, a life-threatening adverse drug experience, inpatient hospitalization or prolongation of existing hospitalization, a persistent or significant disability/incapacity, or is a congenital anomaly/birth defect.Unanticipated Problems Involving Risk (UPR): Defined as being (1) unexpected given the research procedures and characteristics of the population, (2) related (or possibly related) to participation in the research and (3) indicative that the research may place the subject or others at a greater risk of harm than was previously known. Examples of possible UPRs for psychotherapeutic interventions: 1. Psychosis or mania2. New onset or clinically significant exacerbation of a psychiatric disorder3. Suicide and suicide attemptsAn incident, experience, or outcome that meets UPR criteria generally will warrant consideration of substantive changes in the research protocol or informed consent process/document or other corrective actions in order to protect the safety. welfare, or rights of subjects or others. Examples of corrective actions or substantive changes that might need to be considered in response to an unanticipated problem include: modification of inclusion or exclusion criteria to mitigate the newly identified risks; implementation of additional procedures for monitoring subjects; suspension of enrollment of new subjects;suspension of research procedures in currently enrolled subjects;modification of informed consent documents to include a description of newly recognized risks; and provision of additional information about newly recognized risks to previously enrolled subjects. Reporting Requirement: All UPRs/AEs/SAEs, regardless of relatedness to the intervention, are to be reported to the local IRB as soon as possible, no later than 10 business days from the date the investigator or research staff becomes aware of the event/problem. Fill out an AE form, SAE form, and/or UPR form, obtain the study PI's signature, and submit to the Hunter IRB. Then forward each AE/SAE/ UPR form to Data Safety Monitoring Board as soon as possible. The study PI will maintain a record of all AEs/SAEs/ UPRs to report to the Hunter IRB in summary or table form at the end of the study. The PI will notify NIMHD of any UPR, AE, or SAE promptly via email. Protocol Deviation/ViolationA protocol deviation or violation is any change, divergence, or departure from the study design or procedures of a research protocol. Investigators are required to conduct their research according to the plans reviewed and approved by the IRB. Instances where this does not occur, either inadvertently due to circumstances beyond the investigator's control, or due to errors of omission or commission by research project staff, must be reported. Reporting Requirement: Fill out a Protocol Deviation/ Violation form, and submit to local IRB within 3 days of the occurrence (one day if there was harm to the participant). Also email the form (with encryption) to the PI and Study Coordinator, who will maintain a record of all Protocol Deviations/Violations to report to the Hunter IRB.
